8.2. Methods and Timing for Assessing, Recording, and Analyzing Safety Parameters

8.2.1. Adverse Events

Any medical condition that is present at the time that the subject is screened should be considered as baseline and not reported as an AE. However, if the condition increases in severity or frequency at any time during the study, it should be recorded as an AE.

All AEs must be graded for severity and relationship to study product based on the Investigator's assessment.

Severity of adverse events will be graded as follows based on the Investigator's assessment unless otherwise specified in Appendix B.:

Mild: Events require minimal or no treatment and do not interfere with the subject's daily activities.

Moderate: Events result in a low level of inconvenience or concern with therapeutic measures. Moderate events may cause some interference with functioning.

Severe: Events interrupt a subject's usual daily activity and may require systemic drug therapy or other treatment. Severe events are usually incapacitating.

8.2.2. Relationship to Study Product

AEs and SAEs must be assessed by the investigator to determine relationship to study product. All AEs must have their relationship to study product assessed using the following terms. In a clinical trial the study product must always be suspect.

- **Definitely Related:** There is a definite probability that the study product caused the adverse event.
- **Possibly Related:** There is a reasonable possibility that the study product caused the adverse event. Reasonable possibility means that there is evidence to suggest a causal relationship between the study product and the adverse event
- **Not Related:** There is not a reasonable possibility that the administration of the study product caused the event

To help assess, the following factors may be considered:

- Temporal relationship of the event to the administration of study product;

- Whether an alternative etiology has been identified;
- Biological plausibility;
- Existing therapy and/or concomitant medications.

8.3. Reporting Procedures

8.3.1. Adverse Events:

AEs not meeting the criteria for “SAEs,” will be captured on the appropriate case report form. Information to be collected for AEs includes event description, time of onset, investigator assessment of severity, relationship to study product, date of resolution of the event, seriousness, and outcome.

All AEs will be followed until resolved or considered stable by the investigator.

8.3.2. Serious Adverse Events

The following procedures will apply to all serious adverse events:

- The Principal Investigator will report any SAE to ICON PVSS within 24 hours of awareness.
- ICON PVSS will perform an initial check of the SAE for missing elements and then inform the ICON MM, and the ISM.
- ICON PVSS will record the information on the appropriate serious adverse event report form and send to DOD PVG and to Ology Bioservices
- Each SAE will be reviewed and followed to resolution or stability by a study physician
- SAEs will be collected on each subject until his/her last study visit.

Any AE that meets a protocol-defined serious criterion must be submitted immediately (within 24 hours of site awareness) on an SAE form to Ology Bioservices at the following address:

ICON PVSS

ICON plc PVSS

**[name]
[name]
SAE Email Address: [contact]**

ICON Medical Monitor:

[name]

ICON Early Phase Services

[name]
[name], USA
SAE [contact]
SAE Email Address: [contact]

ICON PVSS will send AE/SAE information to Ology Bioservices, Inc.

Ology Bioservices	Ology Bioservices, Inc.
	[name]
	[name], USA
	SAE [contact]
	SAE [contact]
	SAE Email Address: [contact]

Other supporting documentation of the event may be requested by Ology Bioservices and should be provided as soon as possible.

ICON plc PVSS will send SAEs with the ICON Drug Safety Physician assessment of causality, expectedness, and any impact on the benefit-risk ratio of the IMP to Ology Bioservices and DOD PVG. The ICON medical monitor and clinical project manager will be notified of the SAE by DOD PVG. The ICON medical monitor will review and assess the SAE for potential impact on study subject safety and protocol conduct.

At any time after completion of the study, if the investigator becomes aware of an SAE that is suspected to be related to study product, the investigator will report the event to ICON PVSS.

8.3.3. Regulatory Reporting

Following notification from the investigator, Ology Bioservices, the IND sponsor, will report any suspected adverse reaction that is both serious and unexpected to the FDA. Ology Bioservices will report an adverse event as a suspected adverse reaction only if there is evidence to suggest a causal relationship between the drug and the AE. Ology Bioservices will notify FDA and all participating investigators (i.e., all investigators to whom the sponsor is providing drug under its INDs or under any investigator's IND) in an IND safety report of potential serious risks from clinical trials or any other source, as soon as possible, but in no case later than 15 calendar days after the sponsor determines that the information qualifies for reporting as specified in 21 CFR Part 312.32. Ology Bioservices will also notify FDA of any unexpected fatal or life-threatening suspected adverse reaction as soon as possible but in no case later than 7 calendar days after the sponsor's initial receipt of the information. Relevant follow up information to an IND safety report will be submitted as soon as the information is available. Upon request from FDA, Ology Bioservices will submit to FDA any additional data or

information that the agency deems necessary, as soon as possible, but in no case later than 15 calendar days after receiving the request.

All SAEs designated as “not related” to study product(s), will be reported to the FDA at least annually in a summary format.

8.3.4. Reporting of Pregnancy

Pregnancies that occur during the study period will be reported to the Sponsor on the Pregnancy Report form within five days of site awareness.

Efforts will be made to follow all pregnancies occurring prior to 56 days post product administration through to outcome, as described in the Safety Management Plan (e.g. delivery, spontaneous abortion or therapeutic abortion).

8.4. Type and Duration of Follow-up of Subjects after Adverse Events

AEs will be followed until resolution or stability even if this extends beyond the study-reporting period. Resolution of an AE is defined as the return to pretreatment status or stabilization of the condition with the expectation that it will remain chronic.

Follow-up procedures, evaluations, and outcomes will be recorded on the subject's case report forms.

8.5. Halting Rules

8.5.1. Halting Criteria for the Study

Study dosing can be halted at any time if medically indicated. Study dosing must be stopped, and a review of available safety data will be conducted by the SRC if any of the following occur:

1. Death of a dosed subject following injection and prior to the subject's last visit that was not the result of trauma or accident, and possibly related to study product.
2. Occurrence of a life-threatening allergic/hypersensitivity reaction (anaphylaxis) in any subject, manifested by bronchospasm with or without urticaria or angioedema or requiring hemodynamic support with pressor medications or mechanical ventilation.
3. One subject with an SAE.
4. Two or more subjects with a Grade 3 AE in the same organ class (systemic toxicity, clinical laboratory tests or vital signs) regardless of relatedness to study drug. An exception to this includes scenarios where there are obvious and acceptable physiological explanations for a Grade 3 abnormality (e.g., Grade 3 hematuria in a menstruating female).

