	
 • Samples collected to evaluate presence of anti-drug antibodies (ADA) collected for all cohorts. 
 ○ Samples will be tested for ADA at pre-dose and on Days 15, 30, 45, 60, 90, and 120 for Cohorts 1-3. ○ Samples will be tested for ADA at pre-dose and on Days 45, 60, 90, 120, and 180 for Cohort 4.
Estimated Time to Complete Enrollment:	Approximately 5 months.
Description of Study Design:	
A Phase 1, randomized, double-blind, placebo-controlled dose escalation trial of four dose cohorts outlined below:
 
 • Cohort 1: 10 mg IM injection (8 active, 2 placebo) • Cohort 2: 25 mg IM injection (8 active, 2 placebo) • Cohort 3: 50 mg IM injection (8 active, 2 placebo) • Cohort 4: 100mg IM injection (8 active, 2 placebo) 
Dosing for each cohort is as follows: Two sentinel subjects will be administered a single IM dose (one G03-52-01, one placebo). The dosing of the remaining eight subjects within that cohort will not be initiated until at least 24 hours have passed and no adverse events have occurred that meet halting criteria, and no safety signals have occurred that in the opinion of the investigator warrant further investigation. The remaining eight subjects in the cohort will be admitted as scheduled without delay. Dose escalation will not occur until safety data through Day 8 is reviewed by the Safety Review Committee (SRC) composed of the Principal Investigator (PI), Ology Bioservices Medical Monitor, and the ICON Medical Monitor. Objective dose-escalation criteria and safety evaluations will be utilized. A SRC meeting will be held at any time during the course of the study if halting criteria are met or safety concerns arise.
 
The study will consist of a twenty-eight-day screening period and up to 12-hour clinic stay. Follow-up visits will occur at 24 hours, 48 hours, and 72 hours post dose and on Days 4, 8, 15, 30, 45, 60, 90, and 120 for Cohorts 1-3. Follow-up visits for subjects in Cohort 4 will occur at on Days 1, 2, 4, 8, 15, 30, 45, 60, 90, 120, and 180.
 
Subjects will be screened for Human Immunodeficiency Virus (HIV), Hepatitis B surface antigen (HBsAg), and antibody to Hepatitis C virus (HCV), drugs and alcohol. Safety parameters include physical examination, 12-lead Electrocardiogram (ECG), vital signs, and clinical laboratory values to include:

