8.5.2. Dose Escalation Halting Criteria

If any of the following criteria are met, escalation to the next planned dose cohort will not proceed until all available study data have been reviewed by the SRC.

- More than 25% of the subjects in the cohort experience an AE, grade 2 or above in the same organ class
- A specific AE increases in severity from one cohort to the next AND the number of subjects reporting that AE (at the higher severity level) in the cohort is the same or greater. An exception would be headaches going from a grade 1 to a grade 2.

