8.6.4. Safety Review Committee (SRC)

The SRC will be composed of:

- PI, or designee
- Ology Bioservices Medical Monitor
- ICON Medical Monitor or designee;

Objective dose-escalation criteria and safety evaluations will be utilized. For Cohorts 1, 2, and 3 the SRC will evaluate unmonitored and uncoded safety and tolerability data for at least 7 subjects out to Day 8 to determine whether dose escalation can occur. If none of the events described in 9.5.1 Study Halting Criteria or in 9.5.2 Dose Escalation Halting Criteria are observed, dose escalation will proceed. Should any of the study halting criteria or dose escalation halting criteria be met, the SRC will meet to evaluate the data and recommend appropriateness of further dosing. The SRC recommendation to advance to the next level will be documented and provided to all the appropriate parties (PI, Ology Bioservices, ICON and DOD) involved with the study.

If 2 or more subjects withdraw prior to Day 8, those subjects need to be replaced to ensure that data for at least 7 subjects is available for review.

If 2 or more subjects withdraw prior to Day 60 or are not compliant with all PK draws through Day 15, they may be replaced.

If more than 2 subjects withdraw following the Day 8 SRC review of safety data, the site will attempt to replace those subjects in that dose group at the time of the next planned cohort.

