Diarrhea	2-3 loose or watery stools or <400 g/24 hours	4-5 loose or watery stools or 400-800 g/24 hours	≥6 loose or watery stools or >800g/24 hours OR requires IV hydration OR requires medical intervention
REACTOGENICITY			
LOCAL REACTIONS	Mild (Grade 1)	Moderate (Grade 2)	Severe (Grade 3)
Pain – experienced without touching the injection site (spontaneous discomfort)	Does not interfere with activity	Repeated use of non-narcotic pain reliever >24 hours OR interferes with activity	Any use of narcotic pain reliever OR prevents daily activity
Tenderness – hurts only when injection site is touched, or the arm is moved	Discomfort only to touch	Discomfort with movement	Significant discomfort at rest
Pruritus (Itching)	Does not interfere with daily activity	Interferes with daily activity	Prevents daily activity
Ecchymosis (Bruising)*	Does not interfere with daily activity	Interferes with daily activity	Prevents daily activity
Erythema (Redness)*	Does not interfere with daily activity	Interferes with daily activity	Prevents daily activity
Induration (Hardness)/Swelling*	Does not interfere with daily activity	Interferes with daily activity	Prevents daily activity
Nodule	Does not interfere with daily activity	Interferes with daily activity	Prevents daily activity
Ulcer	Does not interfere with daily activity	Interferes with daily activity	Prevents daily activity
Ecchymosis (Bruising)*	25 mm – 50 mm	51 mm – 100 mm	>100 mm
Erythema (Redness)*	25 mm – 50 mm	51 mm – 100 mm	>100 mm
Induration (Hardness)/Swelling*	25 mm – 50 mm	51 mm – 100 mm	>100 mm
Nodule	25 mm – 50 mm	51 mm – 100 mm	>100 mm
Ulcer	1 mm – 50 mm	51 mm – 100 mm	>100 mm
SYSTEMIC REACTIONS	Mild (Grade 1)	Moderate (Grade 2)	Severe (Grade 3)
Allergic Reaction	Pruritus without rash	Localized urticaria OR requires oral therapy	Generalized urticaria; angioedema OR

			anaphylaxis OR requires epinephrine
Headache	No interference with activity	Repeated use of non-narcotic pain reliever >24 hours OR some interference with activity	Significant; any use of narcotic pain reliever OR prevents daily activity OR requires triptans
Fatigue	No interference with activity	Some interference with activity	Significant; prevents daily activity
Myalgia	No interference with activity	Some interference with activity	Significant; prevents daily activity
All Other conditions	Mild (Grade 1)	Moderate (Grade 2)	Severe (Grade 3)

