Illness or clinical AE (as defined according to applicable regulations)	No interference with activity	Some interference with activity not requiring medical intervention	Prevents daily activity and requires medical intervention

*Will not be used as halting criteria

Laboratory and Vital Signs Reference Ranges, Eligibility Ranges, and Toxicity Grading

Laboratory Adverse Events*	Mild	Moderate	Severe	ICON Normal Lab Values
	(Grade 1)	(Grade 2)	(Grade 3)	
Blood, Serum, or Plasma				
Sodium (hyponatremia) – mEq/L	131-132	129-130	<129	133 – 143
Sodium (hypernatremia) – mEq/L	144 – 145	146 – 147	>147	133 – 143
Potassium (hyperkalemia) – mEq/L	5.2 – 5.4	5.5 – 5.6	>5.6	3.5 - 5.1
Potassium (hypokalemia) – mEq/L	3.2-3.4	3.0 – 3.1	<3.0	3.5 - 5.1
Glucose (hypoglycemia) – mg/dL	65 – 69	55 – 64	<55	70 – 105
Glucose (hyperglycemia) – mg/dL Fasting	106 – 125	126 – 200	>200	70 – 105
Blood Urea Nitrogen – mg/dL	21-26	27 – 31	> 31	6 – 20
Creatinine (Male) – mg/dL	1.3 – 2.0	2.1-2.3	>2.3	0.7-1.2
Creatinine (Female) – mg/dL	1.0 – 1.7	1.8 – 2.0	>2.0	0.5 - 0.9
Calcium (hypocalcemia) – mg/dL	8 - <LLN	7.5 – 7.9	<7.5	8.7 - 10.3
Calcium (hypercalcemia) – mg/dL	ULN - 10.8	10.9 – 11.4	>11.4	8.7 - 10.3
CK-U/L	309-1000	1001-1500	>1500	39-308
Albumin (hypoalbuminemia) – g/dL	2.8 – 3.4	2.5 – 2.7	< 2.5	3.5 - 5.2
AST – U/L (Male)	40-97	98-195	>195	<40
AST – U/L (Female)	32-77	78-155	>155	<32
ALT – U/L (Male)	41-100	101-200	>200	<41
ALT – U/L (Female)	33-80	81-160	>160	<33
Alkaline phosphatase – IU/L (Male)	131-260	261-390	>390	40-130
Alkaline phosphatase – IU/L (Female)	106-210	211-315	>315	35-105
Total Bilirubin (serum) – mg/dL	1.3-1.5	1.6-1.9	>1.9	0 - 1.2
Direct Bilirubin – mg/dL	NA	NA	NA	0.0-0.2
Chloride –mEq/L (hypochloremia)	NA	NA	NA	96-108
Chloride –mEq/L (hyperchloremia)	NA	NA	NA	96-108
CO2 –mEq/L (hypo)	NA	NA	NA	20- 30
CO2 –mEq/L (hyper)	NA	NA	NA	20- 30
Total Protein – g/dL	5.5 - 5.9	5.0 - 5.4	<5.0	6.0 - 8.0
Phosphorus- mg/dl (hypo)	2.3-2.4	2.1-2.2	<2.0	2.5 – 4.5
Phosphorus-mg/dl (hyper)	NA	NA	NA	2.5 – 4.5
Total Cholesterol-mg/dl	NA	NA	NA	<201
Triglycerides-mg/dl	NA	NA	NA	<151
HDL – mg/dl	NA	NA	NA	>65 F >55 M

Laboratory Adverse Events*	Mild	Moderate	Severe	ICON Normal Lab Values
	(Grade 1)	(Grade 2)	(Grade 3)	
LDL Direct – mg/dL	NA	NA	NA	<130
Hemoglobin (Male) – g/dL	11.2 - 12.2	10.0 – 11.1	<10.0	12.3-17.3
Hemoglobin (Female) – g/dL	9.8 - 10.8	8.5 - 9.7	<8.5	10.9 - 14.6
WBC Increase – cell/mm ³	10,001– 15,000	15,001 – 20,000	> 20,000	4,000-10,000

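### Read literally, criterion 4 of Protocol 8.5.1 leaves out non-serious Grade 3 injection-site reactions, so two of them do not oblige within-cohort dosing to stop; the gap matters mainly in Cohort 4 and is minor

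*Protocol*

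**What the plan says.** Protocol 8.5.1 is the only list with a compulsory consequence for dosing in progress: "Study dosing must be stopped, and a review of available safety data will be conducted by the SRC if any of the following occur". Its criteria are a possibly related death, anaphylaxis, any SAE, and "Two or more subjects with a Grade 3 AE in the same organ class (systemic toxicity, clinical laboratory tests or vital signs" (the bracket closes there), regardless of relatedness. The same section also permits, but does not require, a halt when medically indicated.

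Appendix B places local and systemic reactions under separate headings. Local reactions run to Grade 3; for injection-site pain this is "Any use of narcotic pain reliever OR prevents daily activity". A starred footnote, "Will not be used as halting criteria", is attached to bruising, redness and induration/swelling. Pain, tenderness, pruritus, nodule and ulcer carry no star.

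Protocol 8.5.2 has no bracket. Its first trigger is "More than 25% of the subjects in the cohort experience an AE, grade 2 or above in the same organ class". Its second is a specific AE that becomes more severe than in the previous cohort, in at least as many subjects. The consequence is that "escalation to the next planned dose cohort will not proceed until all available study data have been reviewed by the SRC". Section 8.5.3 adds that the SRC must agree unanimously, before escalating, that there were no safety signals of any kind. Under 8.6.4, if either set of criteria is met, "the SRC will meet to evaluate the data and recommend appropriateness of further dosing". The Protocol Summary adds: "A SRC meeting will be held at any time during the course of the study if halting criteria are met or safety concerns arise". Section 4 holds the last eight subjects of each cohort for at least 24 hours after the sentinel pair.

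**The concern.** The bracket in criterion 4 names three kinds of event, and local reactions are not among them. Yet starring three local reactions as exempt would be pointless if every local reaction were already outside the halting rules. The footnote therefore suggests that the five unstarred reactions were meant to count somewhere. They can count under 8.5.2, but that section acts on escalation, and nothing follows Cohort 4.

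Local tolerability is a natural question here. The related products were given intravenously (2.2), and dose is raised by changing the volume of a single deltoid injection (5.3, 5.5). At 55 mg per vial, 50 mg needs one vial (50/55 = 0.91) and 100 mg needs two (100/55 = 1.82). That the Cohort 4 volume is larger is an inference, since no volume in mL or reconstituted concentration is given. At stake is whether remaining 100 mg subjects may be dosed after two others had severe injection-site reactions and before the SRC has met.

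**Working it through.** **Route by route, for two non-serious Grade 3 unstarred local reactions in one cohort**

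- 8.5.1, criteria 1-3: not met (no death, anaphylaxis or SAE).
- 8.5.1, criterion 4: not met on a literal reading.
- 8.5.2, first trigger: 2/10 = 20%, which is not more than 25%. A third subject at Grade 2 or above is needed (3/10 = 30%).
- 8.5.2, second trigger: two subjects can meet it, depending on the previous cohort.
- Consequence of 8.5.2: in Cohorts 1-3 the next dose is held; in Cohort 4 the SRC meets under 8.6.4, with no automatic pause.
- Sentinel hold: a compulsory 24-hour wait, but only one sentinel subject is active, so two active cases cannot arise there. Any longer hold rests on the investigator's judgement.

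**How often a stop would act in Cohort 4**

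Inputs: 8 active and 2 placebo subjects, with a sentinel pair of one each (Section 4). The documents give no rate of Grade 3 local reaction, so p is assumed: 5% and 10% as low values, and 15% as the lower end of the any-toxicity range in 10.1. No such reactions are assumed on placebo.

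With X ~ Binomial(8, p):

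- P(X ≥ 2) = 1 − (1−p)^8 − 8p(1−p)^7.
- P(X ≥ 3) = P(X ≥ 2) − 28p²(1−p)^6. Three cases meet the first 8.5.2 trigger with no help from Grade 2 events.

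To find the active subjects spared, suppose that after the sentinel pair the remaining eight (7 active, 1 placebo) are dosed in four pairs. Let A be the active subjects dosed so far and P2(A) the chance of two or more events among them. The expected number spared is the sum, over pairs, of P2(A) times the active subjects in the next pair, averaged over the placebo's position.

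At p = 0.10, P2(2) = 0.0100, P2(3) = 0.0280, P2(4) = 0.0523, P2(5) = 0.0815, P2(6) = 0.1143 and P2(7) = 0.1497. With the placebo in each of the four pairs in turn:

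- first: 2(0.0100) + 2(0.0523) + 2(0.1143) = 0.353
- second: 0.0280 + 2(0.0523) + 2(0.1143) = 0.361
- third: 2(0.0280) + 0.0815 + 2(0.1143) = 0.366
- fourth: 2(0.0280) + 2(0.0815) + 0.1497 = 0.369

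The mean is 0.362. Stopping one pair later replaces the next pair by the one after it.

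| Assumed rate | P(X ≥ 2) | P(X ≥ 3) | Spared, immediate stop | Spared, one-pair lag | Spared, eight dosed together |
|---|---|---|---|---|---|
| 5% | 0.057 | 0.006 | 0.10 | 0.04 | 0 |
| 10% | 0.187 | 0.038 | 0.36 | 0.15 | 0 |
| 15% | 0.343 | 0.105 | 0.73 | 0.32 | 0 |

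The last column is zero because only one active subject is dosed before the eight.

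**Allowing for Grade 2 events**

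The first 8.5.2 trigger also counts Grade 2. If, for illustration, Grade 2 local reactions are as common as Grade 3, the chance of exactly two Grade 3 cases with the other six active subjects below Grade 2 is 28p²(1−2p)^6 = 0.037, 0.073 and 0.074 at 5%, 10% and 15%. Outside that residue, two or more Grade 3 cases would also meet the first trigger and convene the SRC.

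**The case against.** The strongest reply is that the bracket is ambiguous and the footnote points the other way: exempting three local reactions implies that the rest count, so this is a drafting matter. That largely stands. It supports clarifying the text, and it does not show that criterion 4 as written reaches local reactions, because 8.5.2 alone could give the footnote its meaning.

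A second reply is that other safeguards exist. For Cohorts 1-3 this stands: 8.5.2 holds the next cohort, and 8.5.3 demands unanimity on no safety signals. For Cohort 4 the SRC meeting and discretionary halt are real, but neither compels a pause before the committee acts.

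Third, leaving non-serious local reactions to judgement is a defensible sponsor choice. Section 2.3.1 calls IM-injection risks minimal, and the rat study in 2.1.3 used IM doses up to 100 mg/kg with injection-site scoring and found nothing adverse. This lowers the expected rate and supports a minor grading.

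Fourth, a new rule would pool unlike events: severe tenderness in one subject and severe itching in another would stop dosing. That is a fair cost, though the result is only a review.

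A reader might go further and infer that severe local reactions can never hold up dosing, or that Cohort 4 is unprotected. The safeguards above rule out both.

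**Conclusion.** The point holds in a limited form, with minor severity. Criterion 4, read literally, does not make two non-serious Grade 3 local reactions a mandatory stop, and the Appendix B footnote leaves the intent unclear. The exposed interval is within-cohort dosing before the SRC meets, mainly at 100 mg.

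The expected benefit of closing it is about 0.04 to 0.36 active subjects at assumed rates of 5% to 10%, and zero if the last eight are dosed together. It rests on pairwise dosing, prompt recognition, no placebo reactions and rates that the documents do not supply. Section 4 allows up to two weeks for dosing a cohort and admits an alternate for each two-subject group, so staggering is plausible but not required.

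A reader might carry the calculation to 30% or 50%, where about 2.1 and 3.6 subjects would be spared with an immediate stop. Those figures should not be relied on. Cohort 4 opens only after 24 active subjects at three lower doses have passed SRC review, and 2.2 says the move to 100 mg also drew on Day 60 blinded interim data. Rates that high would have to appear abruptly at 100 mg.

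**What to change.** Add a criterion 5 to 8.5.1, for all cohorts: *two or more subjects in one cohort with a Grade 3 injection-site pain, tenderness, pruritus, nodule or ulcer as graded in Appendix B, whether or not judged related.* Dosing then stops for SRC review. Keep the exemption for bruising, redness and induration/swelling, and have the footnote name 8.5.1 and 8.5.2 as the rules it modifies. If the sponsor means all local reactions to stay outside the mandatory stop, 8.5.1 should say so.

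The change is protocol wording only. Local reactions are already collected and graded, so no subjects, visits or samples are added. The cost is a possible short pause, with a chance per cohort of about 0.06 at a 5% rate and 0.19 at 10%.
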